#### D. Rationale of the study

Previous clinical evidence has already demonstrated naloxegol's efficacy and safety in the treatment of opioid-induced constipation in the outpatient setting. To our knowledge, there have been no clinical studies that investigated its potential in the perioperative setting. Opioid analgesia has potential downsides including urinary retention, prolonged ileus, which translates to potential prolonged hospital stay and costs. The aim of this study is to test if the novel peripheral opioid receptor antagonist naloxegol is effective in mitigating these opioid-related side effects and reducing duration of hospitalization and overall costs.

#### **1. STUDY OBJECTIVES**

This will be a prospective, randomized, double-blinded study and will be performed at the Cleveland Clinic Foundation. The study group will receive Naloxegol 25 mg to be given once in the morning every day and the control group will receive placebo.

Specifically, the proposed research will have the following aims:

#### A. Primary Aim

To assess whether patients who received Naloxegol have a lower volume of residual urine in bladder.

Hypothesis: Our primary hypothesis is that patients who received Naloxegol 25 mg given once in the morning every day will have lower volume of residual urine in bladder when compared to placebo.

Post-void residual volume will be measured after asking patient to urinate independent of their previous urination. Post-void residual is a measurement of the urine that remains in the bladder less than 30 minutes following voiding that identifies urinary retention.

Ultrasound has been used as an imaging modality to evaluate bladder function, and its use in the perioperative period as a diagnostic tool for POUR has gained popularity in the past decade. Several studies have shown good correlation between the volumes measured by bladder catheterization and by ultrasound.

#### **B.** Secondary Aims

#### Secondary Aim 1:

To evaluate the effect of Naloxegol on other opioid related side effects.

*Hypothesis.* Patients in Naloxegol group have fewer opioid-related side effects than control group. We will use a validated composite outcome, Opioid–Related Symptom Distress Scale (ORSDS), to evaluate opioid-related side effect. ORSDS is 4-point scale that evaluates 3 symptom distress dimensions (frequency, severity, bothersomeness) for 12 opioid related side

effects [53]. ORSDS questionnaire will be administered by a trained research fellow on first, second, and third postoperative mornings while patients remain hospitalized.

## Secondary Aim 2:

To assess whether Naloxegol is associated with lower need for indwelling urinary catheterization.

Hypothesis: Our hypothesis is that patients who received Naloxegol 25 mg given once in the morning every day will have less need of indwelling catheterization determined by the residual volume to be above 400 ml when compared to placebo.

## Secondary Aim 3:

To assess whether Naloxegol is associated with improved quality of recovery, as measured by the 15-item Quality of Recovery scale.

Hypothesis: Our hypothesis is that patients who received Naloxegol 25 mg given once in the morning every day will have improved quality of recovery. Quality of recovery in the postoperative period is an important measure of the early postoperative health status of patients, and the 15-item Quality of Recovery scale is a validated and efficient measure[32]. Patients will be questioned on the morning of postoperative day (POD) 2 or day of discharge (whichever comes earlier).

## C. Exploratory Aims

## Exploratory Aim 1:

To assess patient satisfaction with the quality of recovery.

Hypothesis: Our hypothesis is that patients who received Naloxegol 25 mg given once in the morning every day will have improved satisfaction with the quality of recovery, as measured on a subjective 100-point scale (where 0 means not satisfied at all and 100 means completely satisfied).

## Exploratory Aim 2:

To assess the effect of Naloxegol on opioid-related prolongation of hospital stay after surgery.

*Hypothesis*. Patients in control group will have prolonged length of hospital stay compared to Naloxegol patients due to opioid-related adverse events.

#### 2. STUDY DESIGN and METHODS

#### A. Study Overview

We propose to assess the effect of Naloxegol on reversing opioid-related side effects in patients recovering from elective primary hip surgery under spinal anesthesia who will be randomly assigned to oral Naloxegol or placebo for two postoperative days or until the date of discharge, whichever occurs earlier (**Table 1**). The design will be a randomized, double-blind, placebo-controlled trial of oral Naloxegol in adults having elective primary hip or knee surgery under spinal anesthesia. The study will be performed at the Cleveland Clinic hospitals.

	Preopera tive visit	Morning of surgery	During surgery	PACU*	POD** 1	POD 2	Day of discharge	
Screening for eligibility	Х	Х						
Consenting	Х							
Baseline medical, demographics, Apfel score, Patient functionality and drug history	Х	х						
Pertinent blood studies (laboratory)	Х				Х	х		
AE/SAE collection		Х			Х	Х		
Study drug (in morning, 1 hr before or 2 hr after meal)		Х			х	х		
Bladder scan at least 2 hours after study drug (morning)					х	Х		
Bladder scan (evening)				Х	х	Х		
Intraoperative record data collection			Х					
Opioid–Related Symptom Distress Scale (ORSDS)					х	х	Х	
Opioid complications survey***				X	х	Х	х	
Numerical pain score				Х	Х	Х	Х	Х
Quality of recovery survey							Х	

Table 1: study flowchart.(Detailed information will be in the CRF's)

\* PACU = post-anesthesia care unit

\*\* POD = post-operative day

\*\*\* Opioid complications survey includes nausea, vomiting, itching, ileus, anti-emetic use, antipruritic use, anti-opioid use

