Type of opioids used and delivery methods seem to affect the POUR as well. Studies that evaluated orthopedic patients who received fentanyl (short half-life) for post-operative analgesia noted that these patients experienced significantly less risk for urinary retention than those who received morphine (intermediate half-life). Several authors have demonstrated that the risk of retention is also increased in patients using PCA compared to those receiving intermittent IV or IM opioids.

Although the cause of POUR is multifactorial and depends on type and duration of surgery as well as existence of comorbidities, systemic opioids are an important risk factor. Urinary retention requires urethral catheterization and potentially indwelling catheter, leading to patient discomfort, hemorrhage, and increased risk of UTI. Urinary catheters can provide an opportunity for gram negative bacterial infections that can lead to further urological and infectious manifestations (e.g. pyelonephritis, urosepsis, death).[15] Catheter-related UTI is responsible for 13% of 100,000 nosocomial infection related deaths each year.[16] It affects about one million Americans annually and is a significant source of morbidity and mortality. It is the most common "preventable" nosocomial infection that accounts for over \$400 million spent annually in the U.S. alone.[15, 17] Bacteria causing the UTI can potentially hematogenously spread and lead to surgical site infection.[18] Bacterial seeding from UTI is a special concern after certain type of surgery, especially those with prosthetic hardware implanted. For instance, ample evidence related UTI with deep joint infection, hemiarthroplasties and total hip arthroplasties in orthopedic procedures, which carries significant morbidity and financial costs. There is currently no effective medical treatment for POUR from opioids. Previous trials of using phenoxybenzamine to treat POUR have shown mixed results.[19, 20] Naloxone had been tried in the past its reversal of analgesia has limited its usefulness in the clinical setting.[21] Furthermore, naloxone's short half-life of 1-1.5 hours is outlasted by the opioids' effects on the bladder. There is a need for an effective treatment to for urinary retention without mitigating the analgesic effects of opioids.[22]

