## **B.** Setting and Population

## i. Inclusion criteria

For inclusion in the study subjects should fulfill the following criteria:

- 1. Provision of informed consent prior to any study specific procedures
- 2. Female or male aged at least 18 years
- 3. American Society of Anesthesiologists physical status 1-4;
- 4. Scheduled for elective primary or revision hip or knee surgery under spinal or general anesthesia;
- 5. Expected to have significant postoperative pain requiring administration of opioids
- 6. Negative pregnancy test

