#### E. Protocol

Patients must meet all inclusion and exclusion criteria to be eligible for the study. After eligibility is confirmed, patients will receive complete information about the study both verbally and in writing. Informed consent must be obtained from the patients prior to randomization and study-specific procedures.

Anesthetic management will follow pre-established clinical and institutional guidelines. Patients can be pre-medicated and will receive spinal or general anesthesia per institutional routine according to attending anesthesiologist discretion. Spinal anesthesia will include the standard monitoring for the given operation, and will occur after the electrocardiogram and monitoring equipment are placed on the patient. Prophylactic antibiotics will be given per surgical routine. During the induction of general anesthesia, indwelling urinary catheters will be inserted only in the patients with operation time exceeding 3 h or who required meticulous monitoring of the intraoperative fluid status. Intraoperative and postoperative fluid management will be left to discretion of the clinicians, who will be administrating them using institution standards.

Randomization (1:1) will be web-based and initiated prior to conclusion of surgery; allocation will thus be concealed from investigators. Randomization will be stratified based on chronic opioid use (if present) to ensure balance between treatment groups within chronic opioid users and nonusers. Chronic opioid use will be defined as opioid use for more than 30 consecutive days, at a daily dose of 15 mg or more of morphine or equivalent, within the 3 months before surgery. The treatment groups will be oral Naloxegol and placebo.

Naloxegol or placebo will be administered starting the first morning of surgery and continued for two postoperative days or until hospital discharge (whichever occurs first) with 25 mg (or equivalent size and shape of Placebo). The post-operative study drug doses will be given in the morning 1 hour before or 2 hours after the morning meal. Intraoperative and postoperative pain medications will be left to discretion of the anesthesiologist.

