#### G. Data Analysis

Naloxegol group and placebo group will be compared for balance of baseline characteristics using standard descriptive statistics (i.e., mean  $\pm$  standard deviation, median [Q1, Q3], or N (%) as appropriate) and standardized difference. The standardized difference is the difference in means or proportions divided by the pooled standard deviation. Any covariable with a standardized difference greater than 0.2 in absolute value will be regarded as a potential confounder, and will be adjusted for when comparing Naloxegol and placebo groups on all the outcomes.

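### The Study Overview lags behind the widened eligibility criteria, and the primary model adjusts for anaesthesia type and primary/revision surgery only if chance imbalance exceeds 0.2; fixing both as covariates is a cheap gain in precision

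*Combined protocol and SAP*

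**What the plan says.** Section A (Study Overview) gives the population twice. The first sentence has "patients recovering from elective primary hip surgery under spinal anesthesia who will be randomly assigned to oral Naloxegol or placebo"; the next has "adults having elective primary hip or knee surgery under spinal anesthesia". Both are limited to primary surgery and spinal anaesthesia.

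Section B.i (Inclusion criteria), item 4, is wider: "Scheduled for elective primary or revision hip or knee surgery under spinal or general anesthesia". Section E (Protocol) agrees with item 4, since patients "will receive spinal or general anesthesia per institutional routine according to attending anesthesiologist discretion".

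On allocation, section E states: "Randomization (1:1) will be web-based and initiated prior to conclusion of surgery". The only stratification factor is chronic opioid use.

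On data, section F (Measurements) names operation time and surgery type among the items taken from the medical record. It does not name anaesthesia type. Table 1 has a general row for intraoperative record data and leaves the detail to the CRF.

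On adjustment, section G (Data Analysis) states: "Any covariable with a standardized difference greater than 0.2 in absolute value will be regarded as a potential confounder". Such covariables are then adjusted for. The primary analysis always includes residual volume before the procedure, plus whatever baseline characteristics turn out imbalanced. No other covariate is fixed in advance.

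On prognosis, Introduction section A states that "the cause of POUR is multifactorial and depends on type and duration of surgery as well as existence of comorbidities".

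**The concern.** The summary of changes shows that Version 2 added revision arthroplasties and general anaesthesia to the inclusion criteria, and that Version 4 revised the Overview only for knee surgery. The current Overview therefore describes a narrower trial than the one being run, and a reader who relies on it would misjudge the population to which the result applies.

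The statistical point is that a more mixed population was admitted without a matching change to the model. The protocol itself ties urinary retention to the type and duration of surgery. It also ties general anaesthesia to catheter placement at induction in some patients. If either factor is prognostic for residual volume, leaving it out enlarges the standard error. A chance imbalance below the 0.2 threshold also stays in the treatment estimate. Whether the factor is adjusted for at all is decided by the observed imbalance and not by the plan.

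**Working it through.** **1. The plan's own figure.** Section H gives 62 per group, 90% power, two-sided alpha 0.05, effect size 0.4 SD, and 4 measurements with correlation 0.3. Assume equal correlation between any two measurements.
- Variance factor for a patient's mean: (1 + 3 × 0.3)/4 = 0.475.
- n per group = 2 × ((1.960 + 1.282)/0.4)² × 0.475 = 131.34 × 0.475 = 62.4. This reproduces 62; power at 62 is 0.898.
- Planned standard error of the group difference: √(2 × 0.475/62) = 0.124 SD.

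**2. How often the 0.2 rule is triggered by chance.** For a binary factor that is not stratified, the standardized difference has SD of about √(4/N).

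| N | SD | P(absolute difference > 0.2) | Left out of the model |
|---|---|---|---|
| 124 | 0.180 | 0.265 | 73% |
| 136 | 0.171 | 0.244 | 76% |

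A binomial simulation with factor prevalence of 10-50% gave 24-28%.

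**3. Shift in the estimate when the factor is left out.** Two inputs are assumptions, because the documents give neither: share under general anaesthesia p = 0.2 to 0.5, and difference in residual volume between anaesthesia types δ = 0.3 to 0.8 SD. The shift is (standardized difference) × √(p(1−p)) × δ.
- Typical case. Given that the absolute difference is below 0.2 (N = 124), its mean is about 0.09. Low end: 0.09 × 0.4 × 0.3 = 0.011 SD. High end: 0.09 × 0.5 × 0.8 = 0.036 SD. That is 3-9% of the 0.4 SD design effect.
- At the threshold. Low end: 0.2 × 0.4 × 0.3 = 0.024 SD. High end: 0.2 × 0.5 × 0.8 = 0.080 SD. That is 6-20% of the design effect, or 0.2-0.65 of one standard error.

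The shift can go either way and averages zero over randomizations.

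**4. Precision.** A difference that persists over all of a patient's measurements adds v = p(1−p)δ² to the between-patient variance: 0.16 × 0.09 = 0.014 at the low end, 0.25 × 0.64 = 0.160 at the high end.
- If v comes on top of the planned variance and is not adjusted for, the variance factor is 0.489 to 0.635. Power at 62 per group is then 0.889 to 0.798, and 65 to 84 per group would be needed for 90%.
- If v is already inside the planned variance, adjusting for it leaves 0.461 to 0.315, and power rises to 0.907 to 0.978.

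The low end is negligible and the high end is not. The documents do not say which is nearer the truth.

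**The case against.** **Eligibility.** A reader might infer that the status of a revision or general-anaesthesia patient is undetermined. The documents do not support that. Section E requires patients to meet the inclusion and exclusion criteria, so criterion 4 governs, and section E's text on anaesthesia agrees with it. The Overview is a summary that was not fully updated. This stands; on its own the mismatch is editorial.

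**Control of the factor.** A reader might also infer that these factors are uncontrolled and that the comparison is biased. Allocation is randomized 1:1, which balances both in expectation, and the standard error already reflects chance imbalance. The 0.2 rule adds conditional adjustment if the factor is recorded as a baseline covariable. This stands too; what is lost is precision, not validity.

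**Data collection.** Absence from section F does not show that anaesthesia type goes unrecorded. Table 1's intraoperative row and the CRF, which is not part of the documents, may cover it. Surgery type is listed and may already separate primary from revision.

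**Prognostic relevance.** Support for an anaesthesia effect is thin. The Introduction names type and duration of surgery and comorbidities, not anaesthesia. The catheter text in section E turns on operation time or fluid monitoring, and operation time is recorded. Four of the scans in Table 1 fall on postoperative days 1 and 2, and nothing in the documents shows an anaesthesia effect lasting that long. This limits the expected gain, but it does not argue against an adjustment that costs almost nothing.

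**Generality.** Preferring fixed to imbalance-triggered adjustment is a criticism that could be made for any covariate. That is fair. These two are singled out because the criteria were widened along exactly these lines.

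**Conclusion.** The point holds as a cheap improvement. The Overview must be reconciled with inclusion criterion 4 and section E. The primary model would also be better with both factors fixed in advance than with a rule that leaves any given binary factor out in about 73-76% of trials.

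The size is modest. The typical unadjusted shift is 0.01-0.04 SD and the ceiling about 0.08 SD, against a standard error of about 0.12 SD. The precision effect ranges from trivial to about ten points of power. All of this rests on an assumed 20-50% share of general anaesthesia and an assumed 0.3-0.8 SD effect. No figure stated in the plan is shown to be wrong.

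**What to change.** 1. Bring both population sentences of the Study Overview into line with inclusion criterion 4 and section E.
2. In section F, name planned anaesthesia type (spinal or general) as a recorded item, fixed before randomization. Planned type is preferable to actual type because the first dose is given on the morning of surgery and the anaesthesiologist chooses the technique, so the actual type may be settled after treatment has begun. Confirm that the surgery type field separates primary from revision.
3. In section G, add planned anaesthesia type and procedure (primary or revision) as fixed covariates in the primary mixed model, whatever imbalance is observed.

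The cost is protocol wording, one data field and about two degrees of freedom, with no additional patients or procedures. The downside is that little is gained if the two factors prove only weakly prognostic.

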## **B.** Setting and Population

## i. Inclusion criteria

For inclusion in the study subjects should fulfill the following criteria:

- 1. Provision of informed consent prior to any study specific procedures
- 2. Female or male aged at least 18 years
- 3. American Society of Anesthesiologists physical status 1-4;
- 4. Scheduled for elective primary or revision hip or knee surgery under spinal or general anesthesia;
- 5. Expected to have significant postoperative pain requiring administration of opioids
- 6. Negative pregnancy test

## ii. Exclusion criteria

Subjects should not enter the study if any of the following exclusion criteria are fulfilled:

- 1. Severe hepatic impairment, with/or twice the upper normal levels of liver enzymes
- 2. Severe renal impairment, or creatinine level > 2.0
- 3. History of bladder cancer
- 4. Patients receiving perioperative regional anesthesia blocks
- 5. Presence of a sacral nerve stimulator
- 6. Medications (anticholinergic), conditions or comorbidity causing urinary retention
- 7. Patient with planned requirement of indwelling urinary catheter insertion before or immediately post-surgery due to immobility
- 8. Urinary Tract Infections and other urogenital comorbidity (incontinence, cysto-ureteric reflux, known bladder retention) or conditions which can cause urinary retention
- 9. Severe peptic ulcer disease, diverticular disease, infiltrative gastrointestinal tract malignancies, or peritoneal metastases

- Patients with known or suspected disruption of blood brain barrier, which may include but not limited to: Alzheimer's disease, stroke, poliomyelitis, cerebral palsy, multiple sclerosis, spinal lesions, and Parkinson's disease
- 11. Gastrointestinal obstruction/Gastrointestinal perforation
- 12. Strong CYP3A4 inhibitors (some antibiotics, antifungals, protease inhibitors, and antidepressants), Strong CYP3A4 inducers, Other opioid antagonists
- 13. Hypersensitivity to MOVANTIK (naloxegol) or any of its excipients

#### C. Withdrawal Criteria

Patients will be free to withdraw from study at any time. Withdrawn patients will no longer receive study drug but will be contacted for follow up and safety checks if patient allows.

#### **D.** Administration of Naloxegol

The investigational drug for this study is Naloxegol 25 mg per dose to be given once in the morning every day (morning of surgery & on postoperative days- 1 hour before or 2 hours after the morning meal ). The placebo control is equal in size, shape, and color to the active tablets and administered according to the same protocol. The Pharmacy team will have the appropriate randomization in case of a safety or emergency situation, and the study drug label will mention that it is "Naloxegol or Placebo".

#### E. Protocol

Patients must meet all inclusion and exclusion criteria to be eligible for the study. After eligibility is confirmed, patients will receive complete information about the study both verbally and in writing. Informed consent must be obtained from the patients prior to randomization and study-specific procedures.

Anesthetic management will follow pre-established clinical and institutional guidelines. Patients can be pre-medicated and will receive spinal or general anesthesia per institutional routine according to attending anesthesiologist discretion. Spinal anesthesia will include the standard monitoring for the given operation, and will occur after the electrocardiogram and monitoring equipment are placed on the patient. Prophylactic antibiotics will be given per surgical routine. During the induction of general anesthesia, indwelling urinary catheters will be inserted only in the patients with operation time exceeding 3 h or who required meticulous monitoring of the intraoperative fluid status. Intraoperative and postoperative fluid management will be left to discretion of the clinicians, who will be administrating them using institution standards.

Randomization (1:1) will be web-based and initiated prior to conclusion of surgery; allocation will thus be concealed from investigators. Randomization will be stratified based on chronic opioid use (if present) to ensure balance between treatment groups within chronic opioid users and nonusers. Chronic opioid use will be defined as opioid use for more than 30 consecutive days, at a daily dose of 15 mg or more of morphine or equivalent, within the 3 months before surgery. The treatment groups will be oral Naloxegol and placebo.

Naloxegol or placebo will be administered starting the first morning of surgery and continued for two postoperative days or until hospital discharge (whichever occurs first) with 25 mg (or equivalent size and shape of Placebo). The post-operative study drug doses will be given in the morning 1 hour before or 2 hours after the morning meal. Intraoperative and postoperative pain medications will be left to discretion of the anesthesiologist.

In the PACU and postoperative periods, patients will be managed at the discretion of the primary care team and the staff anesthesiologist. The need for straight catheterization in PACU and/or on the floor when it is medically indicated (volumes exceeding 400 ml) will be recorded by the study team and subsequent bladder scan will therefore not be done. Postoperatively, all patients will be given intravenous or oral opioids for pain control. Clinicians will adjust analgesic management as necessary in an effort to adjust verbal response pain scores to less than 4.

Clinical evaluators for the outcomes will be blinded to group allocation and Pharmacy personnel not involved in evaluations will prepare the study drugs. Clinicians including nurses will be blinded to monitoring and will be required to perform their standard of care management after surgery.

